9.2.2. Phase I (Expansion cohorts)

- Eligible population: All patients included without major violation of eligibility criteria.

- Population assessable for efficacy: All patients eligible and for whom the following conditions are satisfied:
 - Received at least one complete or two incomplete treatment cycles,
 - At least one disease measurement recorded not less than six weeks after treatment onset.
- The following patients will also be included in the population assessable for efficacy; they will be considered as "inevaluable for response" for the primary endpoint as per RECIST v1.1 criteria (i.e. objective response under treatment) and not be replaced in the primary efficacy analysis:
 - Any eligible patients who received at least one treatment cycle or two incomplete treatment cycles and experience disease progression or die due to disease progression prior to response evaluation (will be considered as "inevaluable for response" due to early progression).
 - Patients withdrawn due to drug-related toxicity without any tumor assessments after the start of study treatment (will be considered as "inevaluable for response" due to toxicity).
 - Patients who received at least one administration of the treatment AND withdrawn due to significant clinical deterioration of unknown reason AND without any tumor assessments after the start of study treatment (will be considered as "inevaluable for response" due to significant clinical deterioration).
- Safety population: all patients having received at least one (any) treatment administration.

Patient's replacement:

- Any patient not eligible or not assessable for efficacy will be replaced.
- However, any patient who received at least one administration of the study drug will be included in the safety analysis.

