2.1.2 Expansion cohorts

- Eligible population: All patients included without major violation of eligibility criteria.
- Population assessable for efficacy: All patients eligible and for whom the following conditions are statisfied:
 - Received at least one complete or two incomplete treatment cycles,

- At least one disease measurement recorded not less than six weeks after treatment onset.
- The following patients will also be included in the population assessable for efficacy; they will be considered as “inevaluable for response” for the primary endpoint as per RECIST v1.1 criteria (i.e. objective response under treatment) and not be replaced in the primary efficacy analysis:
 - Any eligible patients who received at least one treatment cycle or two incomplete treatment cycles and experience disease progression or die due to disease progression prior to response evaluation (will be considered as “inevaluable for response” due to early, progression).
 - Patients withdrawn due to drug-related toxicity without any tumor assessments after the start of study treatment (will be considered as “inevaluable for response” due to toxicity).
 - Patients who received at least one administration of the treatment AND withdrawn due to significant clinical deterioration of unknown reason AND without any tumor assessments after the start of study treatment (will be considered as “inevaluable for response” due to significant clinical deterioration).
- Safety population: all patients having received at least one (any) treatment administration.

Patient's replacement:

- Any patient not eligible or not assessable for efficacy will be replaced.
- However, any patient who received at least one administration of the study drug will be included in the safety analysis.

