2.3 Dose escalation part/ Assessable for safety

The following patients will not be included in the population assessable for safety (primary analysis) and thus will be replaced:

- Patients who received $\leq 75\%$ RDI (Relative Dose Intensity) for trabectedin OR $\leq 75\%$ RDI for durvalumab over cycle 1, due to drug-related AE not considered as DLT.
- Patients who goes off treatment over cycle 1 for reasons unrelated to toxicity (DLT or any other AE), e.g. progression, lost to follow-up, will be replaced.

Population assessable for safety (primary analysis): all patients who completed the DLT assessment period or who developed DLT are included in the analysis.

CREATION OF A NEW INDICATOR VARIABLE

New binary variable TOL

Label: « Assessable for Safety»

TOL = 1 if the patient is assessable for safety (primary analysis)

TOL = 0 if the patient is not assessable for safety (primary analysis)

Criteria	eFORM variable	Control / program
Patient received $\leq 75\%$ RDI (Relative Dose Intensity) for trabectedin OR $\leq 75\%$ RDI for durvalumab over cycle 1, due to drug-related AE not considered as DLT	CYCLE 1 – DAY 1 AND DAY 2 (WEEK1) TREATMENT Trabectedin DOSE_TRA (dose) VPRE_TRA (volume of preparation) VOL_TRA (administered volume) WHY_TRA (2=AE related to treatment) Durvalumab DOSE_DU VPRE_DU VOL_DU WHY_DU DOSE-LIMITING TOXICITY FORM DLT_CYC OCC_CYC REL_ST	IF Trabectedin $((\text{Dose effectivement reçue VPRE_TRA and VOL_TRA/DOSE_TRA}) \leq 75\% \text{ AND INT_TRA} = 1 \text{ AND WHY_TRA} = 2 \text{ AND DLT_CYC} = 0)$ OR Durvalumab $((\text{Dose effectivement reçue VPRE_DU and VOL_DU / 1120 mg}) \leq 75\% \text{ AND INTER_D} = 1 \text{ AND WHY_DU} = 2 \text{ AND DLT_CYC} = 0)$ THEN TOL = 0
Patient goes off treatment over cycle 1 for reasons unrelated to toxicity (DLT or any other AE), e.g. progression, lost to follow-up	DISCONTINUATION VISIT END OF TREATMENT / end of treatment form DT_SOT DT_EOT EOTREASO DISCONTINUATION VISIT END OF TREATMENT / visit DIS_TRT TRA_EOT DUR_EOT DOSE-LIMITING TOXICITY FORM DLT_CYC AE FORM NUMAE AEVENT DT_AE MAX_INT TRA_MOD DUR_MOD	$\text{DT_EOT-DT_SOT} \leq 21 \text{ days}$ AND EOTREASO NOT IN (4 12) AND DLT_CYC=0 Additional control if $\text{DT_EOT-DT_SOT} \leq 21 \text{ days}$ 
 - Listing Other reason - Listing visit of end of treatment: DIS_TRT / TRA_EOT / DUR_EOT - Listing AE with TRA_MOD IN=3 OR DUR_MOD=3 THEN TOL=0

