2.4 Expansion cohort/ Evaluable for efficacy

- Population assessable for efficacy: All patients eligible and for whom the following conditions are satisfied:
 - Received at least one complete or two incomplete treatment cycles,
 - At least one disease measurement recorded not less than six weeks after treatment onset.
- The following patients will also be included in the population assessable for efficacy; they will be considered as “inevaluable for response” for the primary endpoint as per RECIST v1.1 criteria (i.e. objective response under treatment) and not be replaced in the primary efficacy analysis:
 - Any eligible patients who received at least one treatment cycle or two incomplete treatment cycles and experience disease progression or die due to disease progression prior to response evaluation (will be considered as “inevaluable for response” due to early, progression).
 - Patients withdrawn due to drug-related toxicity without any tumor assessments after the start of study treatment (will be considered as “inevaluable for response” due to toxicity).
 - Patients who received at least one administration of the treatment AND withdrawn due to significant clinical deterioration of unknown reason AND without any tumor assessments after the start of study treatment (will be considered as “inevaluable for response” due to significant clinical deterioration).
- Safety population: all patients having received at least one (any) treatment administration.

CREATION OF A NEW INDICATOR VARIABLE

New binary variable ELI_EFF

Label: « Evaluable for Efficacy »

ELI_EFF=1 if the patient is evaluable for the efficacy analysis

ELI_EFF=0 if the patient is not evaluable for the efficacy analysis

Criteria	eFORM variable	Control
Population evaluable for EFFICACY	ELI_EFF (new variable)	ELI_EFF = 1 IF

 Received one complete or two incomplete treatment cycles 	CYCLE 1 – DAY 1 AND DAY 2 (WEEK1) CYCLE 2 – DAY 1 AND DAY 2 (WEEK1) ADMI_TRA (1=Done) ADMI_DUR (1=Done) VPRE_TRA VOL_TRA VPRE_DUR VOL_DUR INT_TRA INTER_D	Cycle 1 completed $(C1_ADMI_TRA = 1 \text{ and } C1_ADMI_DUR = 1 \text{ and } (C1_VPRE_TRA = C1_VOL_TRA) \text{ and } (C1_VPRE_dur = C1_VOL_dur))$ Or Cycle 1 incomplete and Cycle 2 done $(C1_ADMI_TRA = 1 \text{ and } C1_ADMI_DUR = 1 \text{ and } ((C1_VPRE_TRA \neq C1_VOL_TRA) \text{ or } (C1_VPRE_dur \neq C1_VOL_dur))) \text{ and }$

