		$((C2_ADMI_TRA = 1 \text{ or } C2_ADMI_DUR = 1) \text{ and } (C2_VOL_TRA > 0 \text{ or } C2_VOL_TRA > 0))$ Additional control: Date of start cycle Total dose given during cycle Therapy changes during cycle AND

 one disease measurement recorded not less than six weeks after treatment onset 	TUMOR ASSESSMENT (TUM_CYC) DIS_EVA (1=week 6) DT_MEAC	DIS_EVA =1 and Information on tumor assessment completed and date of tumor assessment OR IF
❖ Received at least one treatment cycle and experience disease progression or die due to disease progression prior to response evaluation after the start of study treatment	CYCLE 1 – DAY 1 AND DAY 2 (WEEK1) ADMI_TRA (1=Done) ADMI_DUR (1=Done) TREATMENT (EOTRT) EOTREASO (1=Disease progression and 12=Disease progression and Adverse event(s)) END OF STUDY (EOS) REA_STUD (3=Death) DT_DEATH CA_DEATH (1= Progression of disease) TUMOR ASSESSMENT (TUM_CYC) DT_MEAC (Date of measurement)	(C1_ADMI_TRA = 1 and C1_ADMI_DUR = 1) Additional control: Date of start cycle Total dose given during cycle Therapy changes during cycle AND $((EOTREASO \text{ in } (1 \text{ 12}) \text{ or } (CA_DEATH=1 \text{ and } EOS_REA = 3)) \text{ and } DT_MEAC \text{ is blank})$ OR IF
❖ withdrawn due to drug-related toxicity without any tumor assessments after the start of study treatment	DISCONTINUATION VISIT TRA_EOT (0=toxicity) DUR_EOT (0=toxicity) TUMOR ASSESSMENT (TUM_CYC) DT_MEAC (Date of measurement)	DT_MEAC is blank AND TRA_EOT =0 or DUR_EOT=0 OR IF
❖ Patients who received at least one administration of the treatment AND withdrawn due to significant clinical deterioration of unknown reason AND without any tumor assessments after the start of study treatment	TUMOR ASSESSMENT (TUM_CYC) DT_MEAC (Date of measurement) DISCONTINUATION VISIT END OF TREATMENT (EOTRT) DT_SOT, DT_EOT (start and end of treatment) EOTREASO (8= General or specific changes in patient's condition) ADVERSE EVENT FORM (AEV) DT_AE, DTENDAE (start and end date) TRA_MOD (3= Definitively stopped) DUR_MOD (3= Definitively stopped) TRA_REL (2= Unrelated) DUR_REL (2= Unrelated)	DT_MEAC is blank EOTREASO = 8

- Safety population: all patients having received at least one (any) treatment administration

CREATION OF A NEW INDICATOR VARIABLE

Patients will be evaluable for safety if they have received at least one treatment administration. (SAF=1).

New binary variable ELI_DLT

Label: « Safety population»

SAF=1 if the patient is assessable for safety

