3.2.2 Expansion cohorts

- Analyses will be conducted separately for sarcoma and ovarian cancer patients.
- Primary efficacy endpoint will be analysed based on the eligible and assessable population:
 - Each patient will be assigned one of the following categories:
 - Complete response
 - Partial response
 - Stable disease
 - Progression
 - Inevaluable for response
 - The rate of objective response (complete or partial response) under treatment will be reported:
 - All eligible and assessable patients will be included in the denominator for the calculation of the objective response rate (ORR).
 - The 95% two-sided confidence limits will be provided for the ORR (binomial law).
 - First endpoint conclusions will be based on the objective response rate ORR for all eligible and assessable patients (section 10.2) after centralized radiological review of the data.
- As regards to the other efficacy endpoints, the analyses will be carried out in the eligible and assessable population:
 - Each patient will be assigned one of the following categories:
 - Complete response
 - Partial response
 - Stable disease
 - Progression
 - Inevaluable for response
 - The rate of best overall response will be calculated as the number of patients alive with the best response (recorded from the start of the treatment) divided by the number of patients eligible and assessable.
 - The 6-month progression-free rate will be calculated as the number of patients remaining alive and progression-free at 6 months from the start of the treatment divided by the number of patients eligible and assessable.
 - The 6-month objective response rate will be calculated as the number of patients alive with complete or partial response at 6 months divided by the number of patients eligible and assessable.
 - The 95% two-sided confidence limits will be provided for the calculated rates (binomial law)
- The safety analysis will be performed on the safety population.
- Quantitative variables will be described using mean and standard deviations if the normality assumption is satisfied, else other descriptive statistics (median, range, quartiles) will be reported.
- Qualitative variables will be described using frequency, percentage and 95% confidence interval (binomial law).
- Survival endpoints will be analysed using the Kaplan-Meier method. The median survival rates will be reported with a 95% confidence interval. Median follow-up will be calculated using the reverse Kaplan-Meier method.

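### The SAP's programming columns for the expansion-cohort ORR do not select the eligible-and-assessable population that its text defines

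*SAP*

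**What the plan says.** **Text.** Protocol 9.2.2 and SAP 2.1.2 and 2.4 define a patient as assessable for efficacy if eligible, sufficiently treated, and with "At least one disease measurement recorded not less than six weeks after treatment onset". Three groups without a usable response assessment stay in the denominator as inevaluable. SAP 3.2.2 states: "Primary efficacy endpoint will be analysed based on the eligible and assessable population". Tables 6.1, 6.2 and 6.4 in SAP 4.3.6 name the same population. SAP 2.1.2 adds: "Any patient not eligible or not assessable for efficacy will be replaced".

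**Programming columns.**
- SAP 2.4 renders the scan criterion as "DIS_EVA =1 and Information on tumor assessment completed and date of tumor assessment". The variable column gives code 1 as week 6. No later visit is accepted and no date threshold is given.
- SAP 3.2.3 heads the expansion ORR table `TOL=1`. `TOL` is created in SAP 2.3 for the dose-escalation part. SAP 3.2.4 lists the same ORR row for the expansion cohorts under `ELI_EFF=1`.
- SAP 2.2.4 builds the eligibility flag `ELI` from non-inclusion flags C1NI to C17NI. SAP 2.2.3 lists an eighteenth criterion, with flag C18NI.
- `ELI=1` is not among the conditions for `ELI_EFF` in SAP 2.4, although the text there limits the population to eligible patients.

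**The concern.** A programmer who follows the control columns will not obtain the population that the text defines, and the SAP gives the primary ORR two different filters. Protocol 9.1.1 (Expansion cohorts) requires 14 eligible and assessable patients per cohort and takes the combination forward on a single response. With a threshold of one, the classification of one patient can settle the conclusion for a cohort. It also determines who is replaced, and so how many patients are treated. The analysis is descriptive, so what is at stake is the go conclusion and the reported ORR, not a p-value.

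**Working it through.** **Inputs.** From Protocol 9.1.1: target ORR 20%, 5% error, 14 patients, go on at least one response. From Protocol 4.7: scans every six weeks, ±7 days. Assumed, because the documents give no figure: true ORRs of 5% and 10% alongside the 20%, and a 5–10% chance that a responder has no week-6 scan but a later one.

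**1. The plan's own figure.** The Gehan first stage takes the smallest n with (1 − 0.20)^n ≤ 0.05. 0.8^13 = 0.055 and 0.8^14 = 0.044, so n = 14, as stated. With only 13 counted, the 5% bound is missed.

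**2. Cases run through text and code.**

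| Patient | Text | Code |
|---|---|---|
| Full cycle 1, no week-6 scan, scan at week 12 | Assessable | `ELI_EFF=0`, replaced |
| Full cycle 1, week-6 visit scanned on day 38 | Under 42 days, so short of the criterion if read literally | `ELI_EFF=1` |
| Breaches criterion 18 only | Not eligible | `ELI=1` |
| Ineligible, full cycle 1, week-6 scan | Not assessable | `ELI_EFF=1` |

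In the first row, the three alternative routes do not rescue the patient. Each needs the measurement date to be blank, reading the toxicity route as its row label intends.

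**3. `TOL` against `ELI_EFF`.** `TOL` tests cycle-1 dose intensity and stopping within 21 days. It has no eligibility test and no scan test, so it cannot reproduce the population in SAP 3.2.2.

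**4. Size of the scan error.** If the dropped patient is the only responder, 1/14 = 7.1% (go) becomes 0/13. A replacement restores the count of 14 but not that response; a go then needs the replacement to respond.

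- P(exactly one response in 14) = 14p(1 − p)^13
- P(and the replacement does not respond) = the above × (1 − p)
- P(lost go) = the above × assumed chance that this responder missed week 6

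| True ORR p | Exactly one in 14 | × (1 − p) | × 5% to 10% |
|---|---|---|---|
| 5% | 0.359 | 0.341 | 0.017–0.034 |
| 10% | 0.356 | 0.320 | 0.016–0.032 |
| 20% | 0.154 | 0.123 | 0.006–0.012 |

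If missing week 6 is unrelated to response and every dropped patient is replaced, the final 14 are still a random set of 14. The average probability of a go over trials is then unchanged. The loss is an observed response in that trial and one more patient treated.

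**5. Conditional: early progressors under `TOL=1`.** SAP 2.3 sets `TOL=0` for "Patients who goes off treatment over cycle 1 for reasons unrelated to toxicity (DLT or any other AE), e.g. progression, lost to follow-up", coded as treatment end minus treatment start of at most 21 days. The efficacy text keeps "Any eligible patients who received at least one treatment cycle or two incomplete treatment cycles and experience disease progression or die" of it before response evaluation. Whether the two collide depends on the treatment-end date. Protocol 4.4 dates discontinuation 30 days after the last dose unless a new antitumour therapy starts sooner. A patient last dosed on day 2 would then end on day 32, which is 32 − 1 = 31 days after the start, and the 21-day test would not apply. The reason code for progression with adverse events is also exempt. If one such patient were removed without replacement, an illustrative 2/14 = 14.3% (exact 95% CI 1.8–42.8%) would become 2/13 = 15.4% (1.9–45.4%), with no change of decision.

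**The case against.** The best reply is that the intent is plain. SAP 3.2.2, the SAP 3.2.4 header and the output tables all point to eligible and assessable patients, and `TOL=1` looks like a header carried over from the escalation table directly above it. Criterion 18 is checked separately in SAP 2.2.3 and matters only if someone is enrolled in breach of it. The sums in question are small and rest on an assumed missed-scan rate.

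Most of this stands as a limit on weight. It does not remove the contradiction. The carry-over explanation concedes an error in the ORR table, and it does not reach the week-6 code, which is the SAP's only operational version of the scan criterion.

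The objection does defeat several stronger readings that a reader might infer:
- *That `TOL=1` certainly removes early progressors.* This depends on how the treatment-end date is entered, which the documents do not say.
- *That the early-progression route wrongly shuts out patients with two incomplete cycles.* It asks for "C1_ADMI_TRA = 1 and C1_ADMI_DUR = 1" with no volume test. The SAP's coded two-incomplete-cycles rule also asks for both drugs in cycle 1, so everyone meeting that rule already passes.
- *That "DT_MEAC is blank AND TRA_EOT =0 or DUR_EOT=0" is a logic error for want of brackets.* Line breaks may have been lost from the PDF, and the row label shows the meaning.
- *That requiring a blank measurement date wrongly drops progressors with an early scan.* This turns on undocumented coding of unscheduled scans, and on whether progression before response evaluation means before any evaluation, which is what the code tests.
- *That accepting days 35–41 is a defect.* Given the ±7-day window, counting the nominal week-6 visit is reasonable. The fault is only that text and code do not say the same thing.

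**Conclusion.** The point holds and should be fixed before the analysis. Three discrepancies are established from the documents alone: the week-6-only scan test, the escalation flag on the expansion ORR table, and an eligibility chain that omits C18NI and is not carried into `ELI_EFF`. They can act in either direction. The scan test can discard a responder; the missing eligibility conditions can keep patients who should be out.

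The size is nil if no such patient arises, and the documents give no frequency. Under the assumed 5–10% missed-scan rate, a lost go has a probability of roughly 0.6–3.4% for true ORRs of 5–20%. A reader might infer that the ORR is systematically biased or that the go decision is unreliable. The documents do not support that: the decision changes only when the misclassified patient is decisive, and the average chance of a go does not move if missed scans are unrelated to response and all drops are replaced. The reason to act is that one response decides the rule and the correction is nearly free.

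**What to change.** 1. In SAP 2.4, require `ELI=1` for `ELI_EFF`, and replace `DIS_EVA=1` with any tumour assessment at the week-6 visit (within its ±7-day window) or later. State the same window rule in the accompanying text, so that days 35–41 are treated alike in both.
2. In SAP 3.2.3, head the expansion ORR table `ELI_EFF=1` instead of `TOL=1`.
3. In SAP 2.2.4, add C18NI = 1 to the conditions that set `ELI=0`.
4. Check against the eCRF coding, without presuming an error: the bracketing of the toxicity route, the coding of unscheduled scans, and the entry of the treatment-end date.

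A bare 42-day cut-off should be avoided. A patient with stable disease on day 38 who then stopped for toxicity would fail the scan test, would also fail the toxicity route because a measurement exists, and would be replaced. Replacing a known non-responder gives 14 chances of a response instead of 13. P(at least one), from 1 − (1 − p)^13 to 1 − (1 − p)^14, then rises from 0.487 to 0.512 at 5%, 0.746 to 0.771 at 10%, and 0.945 to 0.956 at 20%.

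Cost: SAP wording only, with no new data, visits or patients. The reported ORR may move slightly in either direction.

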3.1 Descriptive analysis

All analyses will be descriptive; no p-values will be calculated. Data analyses will be provided by dose groups and for all study patients, combined wherever appropriate. For continuous variables, summary statistics will include number of patients, mean, median, standard deviation, standard error, minimum, and maximum. Categorical endpoints will be summarized using number of patients, frequency, percentages, and standard errors. Missing data will not be imputed.

3.2 Endpoint analysis

3.2.1 Dose escalation part

- Primary endpoint will be analyzed on the population assessable for safety of the phase I trial (escalation part).
- Toxicity observed at each dose level, graded according to the Common Terminology Criteria for Adverse Events v4.0 from the NCI, will be recorded in terms of event type, severity, dates of beginning and end, reversibility and evolution. Data will be gathered in tables summarizing toxicities and side effects for each dose level and cycle.
- DLT will be described in terms of number and incidence rates at each dose level. The number and percentage of patients who will have developed a DLT in each dose level will also be reported.
- Data analyses will be provided by dose groups and for all study patients, combined wherever appropriate.
- Categorical endpoints: best overall response, ORR under treatment and at 6 months, 6-month ORR and 6-month PFR, will be reported in terms of counts by dose level.
- Continuous endpoints will be reported in terms of summary statistics that will include number of patients, median, minimum, and maximum, and additional percentiles if appropriate.
- Survival endpoints (PFS and OS) will be analyzed using the Kaplan-Meier method. The median survival rates will be reported with a 95% confidence interval. Median follow-up will be calculated using the reverse Kaplan-Meier method.

- Missing data will not be imputed.

